15. DATA ANALYSIS

15.1 General Approaches

Compare the effectiveness of the H42-HV program using a remotely-delivered health coaching intervention integrated into home visiting with mHIP-HV among 400 pregnant and postpartum women enrolled from early home visiting programs in Maryland:

- Primary outcome: PPWR at 6 months after delivery
- Maternal secondary outcomes: GWG (37 week minus baseline pregnancy [≤ 15 week gestation] weight); Proportion with excessive GWG.
- Infant secondary outcomes: Weight at birth, 2 months, 4 months, and 6 months of age will be gathered as maternal self-report via online surveys and verified with infant medical records.
- Maternal and infant health care utilization, including receipt of postpartum care, ER visits and routine well infant visits, captured for those participants who are Medicaid recipients using claims data.
- Other outcomes: Maternal health behaviors (diet, physical activity, and breastfeeding); Maternal wellness (depression, sleep, and stress)

The main analyses for the primary and secondary outcomes will follow the ITT principle. The analysis for PPWR will utilize a mixed effects model to assess between group difference in mean of total PPWR.

15.2. Main analytic model for the primary outcome of PPWR (difference between pre-pregnancy weight and weight at 6 months postpartum).

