We will carry out the main analysis to assess the between group difference using a mixed effects model characterized by a mean model relating the outcome to the predictors and a variance-covariance model addressing variance of all available longitudinal weight outcomes and correlation between outcomes measured overtime within individual. The predictors in the mean model will include a group indicator (0 for Group B and 1 for Group A), 3 visit indicators for 2, 4, and 6 months respectively, with 0 for baseline and 1 for the specific month postpartum the visit indicator corresponding to, and the group by visit interaction terms, adjusting for study sites, BMI category, and gestation at the time of enrollment used for randomization stratification, all as fixed effects. The regression coefficient of the group by 6-months postpartum weight interaction term will estimate the primary outcome, i.e., mean difference in PPWR at 6-months between intervention and control groups. We will use an unstructured variance-covariance model to allow full flexibility on outcome variances and correlations. Data from all participants randomized will be used in this analysis, including missing data which will be included using a software specified missing indicator.

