15.3. Secondary outcomes and additional analyses

Analyses for between group differences in GWG and infant weights will be assessed using the same mixed-effects modeling approach with separate models similar to the main model described above. Between group differences in binary outcomes of diet, physical activity, breastfeeding and women's wellness outcomes (depression, sleep, stress, social support) will be described between H42-HV intervention and Control arms using standard cut points for the

scales and modeled using logistic regression model based longitudinal models implemented through generalized estimation equations (GEE) approach employing group indicator, visit indicators, group by visit interaction terms and adjusting for the variable used to stratified the randomization. Robust variance estimate will be used for statistical inferences to derive 95% confidence intervals for the population-average based estimates and corresponding p-values. Conforming to recommended maternal postpartum care utilization and well-baby care utilization over time will separately be modelled using similar GEE approach as described above for the longitudinal binary outcomes.

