16.0. Sample Size and Power Estimates informing Primary Aim

We request approval for enrollment up to 400 participants with the goal of N=360 for power calculations.

Table 6. MDD for PPWR for sample of 360 with 90% power, after 30% random attrition

Power	SD of PPWR (Kg)	Minimum Detectable Difference (MDD) (Kg)
90%	5.5	2.26
90%	7.0	2.87
90%	8.0	3.28
90%	8.8	3.61

With this sample size, our objective is to determine the minimum detectable difference (MDD) for the primary outcome of PPWR between the 2 study groups. Our assumptions are as follows: Two-sided type I α error=0.05; type II β error=0.10; and 70% or greater follow-up for the main outcome of PPWR at 6-months. Based on our past experience and review of the literature, we anticipate <30% loss to follow-up for 6-month weights, consequential to drop-out of various kinds (e.g., lost to follow-up, censored due to new pregnancy). With this dropout rate and the assumption that the dropout is consistent with missing at random,

we expect to retain an effective sample size of 252 participants for our primary outcome, by randomizing N=360 participants, with 126 participants in each arm. Standard deviations for the MDD evaluation were informed by previous studies of similar combined diet-physical activity behavioral interventions to limit weight gain in pregnancy and promote postpartum weight loss^{88,89,90,91}. The MDDs range from 2.3- 3.6 kg with the assumption of 30% random attrition of the proposed sample size of 360. Based on these prior studies effect sizes we believe our sample size calculation in **Table 6** is conservative.

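### Section 15.3 analyses the survey-based binary outcomes by unweighted logistic GEE and states neither a working correlation nor a missing-data method, which is not valid in general under missing at random

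*Combined protocol and SAP*

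**What the plan says.** Section 15.3 of the combined protocol and SAP fits the binary diet, physical activity, breastfeeding and wellness outcomes with "logistic regression model based longitudinal models implemented through generalized estimation equations (GEE) approach". The mean model contains "group indicator, visit indicators, group by visit interaction terms and adjusting for the variable used to stratified the randomization". On inference it says: "Robust variance estimate will be used for statistical inferences to derive 95% confidence intervals for the population-average based estimates". Care utilization is handled likewise: "well-baby care utilization over time will separately be modelled using similar GEE approach".

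No working correlation is named for these models, and no weighting, imputation or missing-data sensitivity analysis. The only missing-data sentence in the analysis section belongs to the primary mixed model in 15.2: "including missing data which will be included using a software specified missing indicator". Section 17 sends removed outliers to the same treatment as other missing data, and its only sensitivity analysis puts those outliers back.

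Section 15.1 states: "The main analyses for the primary and secondary outcomes will follow the ITT principle". Section 16.0, which concerns the primary aim, says "we anticipate <30% loss to follow-up for 6-month weights, consequential to drop-out of various kinds" and continues "With this dropout rate and the assumption that the dropout is consistent with missing at random".

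**The concern.** A correctly specified likelihood-based mixed model, such as the one planned for weight, gives valid estimates when missingness depends on observed data. An unweighted GEE in general does not. It is safe if missingness depends only on covariates in the mean model (here arm, visit and the stratification factors), and nearly safe if the working correlation is close to the truth. The plan commits to neither condition. The robust variance repairs the standard error, not the estimate.

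What matters for the arm comparison is whether the link between earlier answers and later response differs by arm. That is plausible here. Table 4 gives H42-HV women about 7 coaching contacts in pregnancy and about 6 postpartum, while section 5.2.3 adds only a short video to usual home visiting. Under section 12.1.e coaches turn to the home visitor when calls are missed, a channel the comparator lacks. Section 14.1 allows discontinuation for intervention non-compliance, which bears mainly on the coached arm. Participants are unblinded and these outcomes are self-reported.

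At stake is whether a reported arm difference in depression, stress, sleep or behaviour could be told apart from selective survey loss.

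**Working it through.** **1. The plan's own figures.** 360 × (1 − 0.30) = 252, or 126 per arm. The normal approximation (1.960 + 1.282) × SD × √(2/126) gives 2.246, 2.859, 3.267 and 3.594 kg for SDs of 5.5, 7.0, 8.0 and 8.8 kg. The t-based solution gives 2.255, 2.870, 3.280 and 3.608, which matches Table 6 (2.26, 2.87, 3.28, 3.61). All of this concerns weight. The plan gives no loss rate or power for the survey outcomes.

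**2. Why unweighted GEE can fail.** GEE solves Σ D′V⁻¹(Y − μ) = 0 over observed visits. With an independence V and group-by-visit terms (strata set aside), the fitted month-6 value is the proportion among responders, P(Y₆ = 1 | responded, arm). If response depends on the month-4 answer, and that answer is correlated with month 6, this differs from P(Y₆ = 1 | arm).

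**3. Simulation A (assumed inputs).** Visits at baseline, 2, 4 and 6 months. True prevalence 0.40 at every visit in both arms. Exchangeable latent correlation 0.5 or 0.7. Monotone loss per interval:
- Completely at random: 0.112, so retention is 0.888³ = 0.700.
- Same mechanism in both arms: 0.19 after a positive answer, 0.065 otherwise; odds ratio (0.19/0.81)/(0.065/0.935) = 3.4.
- Arm-specific: 0.22 and 0.045 in H42-HV, odds ratio (0.22/0.78)/(0.045/0.955) = 6.0; 0.112 regardless of answer in the comparator.

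Month-6 group-by-visit log odds ratio (truth 0), one million women per row:

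| Loss | Latent correlation | Month-6 prevalence under independence, H42-HV / comparator | Log OR, independence | Log OR, exchangeable |
|---|---|---|---|---|
| At random | 0.5 | 0.401 / 0.400 | 0.005 | 0.006 |
| At random | 0.7 | 0.401 / 0.402 | −0.008 | −0.007 |
| Same in both arms | 0.5 | 0.367 / 0.367 | −0.001 | −0.002 |
| Same in both arms | 0.7 | 0.352 / 0.351 | 0.003 | 0.000 |
| Arm-specific | 0.5 | 0.355 / 0.401 | −0.192 | −0.006 |
| Arm-specific | 0.7 | 0.332 / 0.399 | −0.289 | −0.013 |

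The arm-specific rows under independence are odds ratios of exp(−0.192) = 0.83 and exp(−0.289) = 0.75, or 1.21 and 1.34 read the other way. Inverse-probability weighting with the true loss probabilities returned 0.399 to 0.402 in both arms in all six rows.

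Type I error at N = 360 (latent correlation 0.6, 2,000 replicates, nominal 5%):
- Loss at random: 5.9% independence, 6.0% exchangeable.
- Same mechanism: 5.5% and 5.6%.
- Arm-specific: 15.2% and 5.5%.

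**4. Simulation B (different assumed inputs).** Five visits, prevalence 0.30, no true effect, 28-29% lost in each arm. Latent correlation was exchangeable (0.5 or 0.7) or AR(1) (0.8 or 0.9).
- Loss tied to the previous answer in the comparator only (odds ratio 3-4): 1.13-1.35 under independence, 0.98-1.02 under exchangeable, including the AR(1) cases where exchangeable is misspecified.
- Odds ratio 3 in both arms: 0.99-1.01 under independence.
- Odds ratio 3 in one arm and 2 in the other: 1.05-1.10 under independence.
- Loss tied to a baseline characteristic outside the model: 1.06-1.13 under independence, 1.02-1.04 under exchangeable.

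A further variant with one-sided loss of about 30% gave 1.22-1.27 under independence and 1.04-1.06 under exchangeable.

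**5. Scale.** With 126 per arm and 30% prevalence, the SE of a cross-sectional log odds ratio is √(2/(126 × 0.3 × 0.7)) = 0.275. Odds ratios of 1.13 and 1.35 are log biases of 0.122 and 0.300, or 0.44 to 1.09 SE. An exchangeable result of 1.06 is 0.058, or 0.21 SE.

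**The case against.** A reader might infer that section 15.3 contradicts the plan's own missing-at-random assumption and 30% loss for these outcomes. The documents do not support that. Both statements sit in the power section for the primary aim and refer to 6-month weight; one listed cause of loss, a new pregnancy, is specific to weight. Nothing is stated for the surveys. That the GEE would use available responses only is itself inferred from silence.

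It is also tempting to read the larger odds ratios as the expected bias. They need two things together: loss that depends on earlier answers differently by arm, and an independence working matrix. The plan specifies no such matrix, and the documents give no figure for differential loss. They do describe safeguards: the same phone-assisted survey schedule in both arms (Table 3), blinded data collectors (section 11), monitoring of missing surveys (sections 10 and 17), and a request that women who discontinue complete remaining assessments (section 14.0). With one mechanism in both arms the contrast is essentially unbiased.

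Nor does the concern reach every secondary outcome. Utilization taken from Medicaid claims is much less exposed to survey loss, and gestational weight gain and infant weight use mixed models.

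Finally, exchangeable GEE alone removes most of the bias, so the simulations do not show imputation to be indispensable. All of this stands and limits the size and reach of the point. It does not supply the missing specification.

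**Conclusion.** The point holds in limited form. For the survey-based binary outcomes, the model in 15.3 is not valid in general under missing at random, and the plan leaves open the one choice, the working correlation, that largely decides how much this matters. Under assumed inputs, arm-specific loss with an independence matrix shifts a null odds ratio to roughly 1.1-1.35 in either direction, and type I error reached about 15% in one setting. Under a common mechanism, or with an exchangeable working correlation, little or no bias remains in the arm contrast.

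These figures rest on assumed prevalence, correlation and loss patterns and show direction and range only. The primary result is unaffected. The change should be made because it is inexpensive, uses data already collected, and closes a choice that could otherwise be made after the data are seen.

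**What to change.** In section 15.3, for the survey-based binary outcomes:

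1. Name an exchangeable or unstructured working correlation, and exclude independence for the unweighted model.
2. Name one missing-data method: inverse-probability-of-response weighting, or multiple imputation within arm followed by the planned GEE. Use all observed visits, the baseline value where one exists, and a short list of baseline characteristics such as language, education and wellness scores. Ongoing lactation is measured only after delivery (section 9.3.7), so breastfeeding intention would take the place of a baseline value.
3. Report the unweighted available-case GEE alongside, with response rates by arm and visit.

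No new data are needed. The cost is modest programming and added model assumptions, which the side-by-side report keeps visible. Section 7 lists nine programs as examples of sites, so using site as an imputation predictor within arm may give sparse cells; the predictor set should stay small.

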15.4. Exploratory analyses for heterogeneity of intervention effect

Importantly, we will explore for potential modifiers of intervention effects by conducting subgroup analyses by race/ethnicity, HV program characteristics, baseline BMI category (overweight/obese), language spoken at home, low English proficiency, education level and exploring for effect modification by adding appropriate interaction terms to the primary mixed-effects model. Although we do not expect the main effects to differ, we will explore for the potential of such heterogeneity of intervention effect.

16.0. Sample Size and Power Estimates informing Primary Aim

We request approval for enrollment up to 400 participants with the goal of N=360 for power calculations.

Table 6. MDD for PPWR for sample of 360 with 90% power, after 30% random attrition

Power	SD of PPWR (Kg)	Minimum Detectable Difference (MDD) (Kg)
90%	5.5	2.26
90%	7.0	2.87
90%	8.0	3.28
90%	8.8	3.61

With this sample size, our objective is to determine the minimum detectable difference (MDD) for the primary outcome of PPWR between the 2 study groups. Our assumptions are as follows: Two-sided type I α error=0.05; type II β error=0.10; and 70% or greater follow-up for the main outcome of PPWR at 6-months. Based on our past experience and review of the literature, we anticipate <30% loss to follow-up for 6-month weights, consequential to drop-out of various kinds (e.g., lost to follow-up, censored due to new pregnancy). With this dropout rate and the assumption that the dropout is consistent with missing at random,

we expect to retain an effective sample size of 252 participants for our primary outcome, by randomizing N=360 participants, with 126 participants in each arm. Standard deviations for the MDD evaluation were informed by previous studies of similar combined diet-physical activity behavioral interventions to limit weight gain in pregnancy and promote postpartum weight loss^{88,89,90,91}. The MDDs range from 2.3- 3.6 kg with the assumption of 30% random attrition of the proposed sample size of 360. Based on these prior studies effect sizes we believe our sample size calculation in **Table 6** is conservative.

17. DATA MANAGEMENT

We will use REDCap, a secure, password protected, web-based application for building and managing online surveys and study data. We will ensure data quality through building cross-check, logic check, and range check for data entry and monitoring data collection completion through automatic flags in REDCap. The data manager will conduct thorough data checking and cleaning, including examining distributions and data patterns and running routine reports on run charts and outlier detection scripts, and flagging unusual data values and data inconsistencies for possible correction measures. We will also record and routinely review lag time in data entry, timely issue data queries on missing data, out of range values or illogical data relations and resolve identified data issues, and review types and distribution of data entry errors/issues and remedy any systematic concerns. Confirmed unusual data values and data inconsistencies will be reviewed and adjudicated by the study team to decide possible action and final decision made for any data correction will be documented. All data access and corrections get automatically logged in REDCap data audit trails.

The data manager will also prepare reports regularly for the PI, investigators, staff and the Safety Officer on Quality Control (see Data Safety and Monitoring Plan) for review and to remedy any concerns. Every effort will be made to determine the correctness of outlying values in a timely manner. Confirmed outliers will be flagged and set aside in the primary analysis. Outliers removed will generate a missing data code and be treated as for all other missing data. Sensitivity analyses will be conducted with inclusion of outliers to assess influence on results. The data manager and analyst will create detailed, organized documentation of variables and conduct analyses according to protocol under direction of [name], study biostatistician.

18. DATA SAFETY AND MONITORING PLAN (DSMP)

We have included the DSMP in this IRB application. We will have a DSMB through the parent Center Grant, The Center for Cardiometabolic Health Equity.

19. DATA SECURITY PRIVACY AND PROCESSES

Our protocol was deemed Tier Risk A by the IRB Risk Calculator. We described Data Security and Processes below.

19.0. Data Storage and Analysis

We will store all Medicaid data extracts and all study data with PHI on the SAFE Desktop. We will use REDCap for data collection using surveys and management of study processes. All data analyses will be conducted on the SAFE Desktop. We will limit study staff access to the Desktop only for those who will require access and will remove access rights once this access is no longer required.

19.1. PHI Data on the Web-Based Platform and Study Scale

The web-based platform involves a “back end” build in REDCap, which contains all patient health information. Data from the at-home cellularly enabled study scale (BodyTrace or similar) will be integrated into REDCap using a secure API data transfer via a de-identified token. The user interface will be hosted internally within the Johns Hopkins firewall. We are working to re-create the educational platform and for this study it will be hosted and managed by Johns Hopkins Cloud & Virtualization Services and was developed by a large healthcare IT company called TonicGroup, Inc. It was selected because it has the optimal security measures in place to protect patient privacy. All data on the platform will reside behind the JH firewall. The platform uses standards for data exchange and integration, such as HL7 FHIR and is compliant with all U.S. privacy and security standards for electronic health records. With participant authorization (see above) the platform will integrate REDCap data using a secure API data transfer via a de-identified token. The summary data from the platform will be exported directly into the SAFE desktop.

Although a mobile application will be recommended for participants in the intervention group, no data will be directly transferred to the REDCap database; instead, participants will have the option of self-reporting their data using a unique encrypted REDCap link.

